The Malezi I intervention was found to be feasible and acceptable as an integrated intervention within routine MNCH/PMTCT services. The internal Malezi I program evaluation, using a pre/post design, found substantial increases in caregiver knowledge and practices as reported through exit and household-based interviews. Knowledge among facility-based health providers and CHWs also increased significantly, and health providers reported increased access to ECD resources.

Given the existing and emerging evidence on potential strategies to better engage communities in supporting health promotion interventions, the Malezi II grant will expand Malezi I coverage of CCD program implementation to nearly double the number of facilities supported, and introduce additional components, specifically, a mass media campaign and video job aids. The addition of video job aids aims to further support and improve CHW education and counseling skills, and the addition of radio messaging aims to promote perceptions and knowledge of ECD, and possibly responsive caregiving behaviors, more broadly at the community level.

The Malezi II program, additional multi-media components, and theory of change model informing the evaluation

The Malezi II grant supports a continuation and expansion of the Malezi I CCD program described earlier, plus two additional interventions related to multi-media communications aimed at improving ECD perceptions, knowledge and responsive caregiver behaviors. These two approaches include a mass media communication strategy using radio messaging and the introduction of short video job aids, along with capacity building training for community health workers in the use of those job aids. This study is designed to evaluate the comparative effectiveness of the two interventions with respect to ECD perceptions, knowledge and responsive caregiving outcomes. In addition, by analyzing differences between baseline and endline within each study group (pre/post design), we will describe the effectiveness of radio messaging alone compared to no radio messaging, and the effectiveness of a fully integrated ECD intervention, including radio messaging, short video job aids and Malezi CCD program support compared to CCD program support without radio and short video support.

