- To what extent does the Malezi II radio messaging reach caregivers of young children?
- To what extent are caregiver ECD perceptions, knowledge and reported parenting practices changed after introduction of Malezi II radio messaging to their communities?
- Is there a relationship between reported listenership and/or message recall (dose) and caregiver ECD perceptions, knowledge and reported parenting practices?
- To what extent does exposure to the Malezi II full intervention (MRV-CCD: radio messaging, video job aids, continued CCD program support) improve caregiver knowledge and parenting practices?
- Does exposure to the Malezi II full intervention (MRV-CCD) improve caregiver knowledge and parenting practices significantly more than exposure to radio messaging alone (MR)?
- To what extent do the CHWs adhere to the Malezi II training with regard to use of the video job aids, delivery of complete and accurate ECD messages, and general quality of counseling support?
- Do the Malezi II video job aids improve the quality of CHW ECD counseling support given to caregivers in clinic and home settings?

METHODOLOGY

This study is a two-arm quasi-experimental pre-post evaluation design, comparing two interventions to establish their relative impact on caregiver knowledge and behaviors/practices among a cohort of caregivers of children 0-24 months at enrolment (baseline) and under three years after a 9-month

intervention exposure period (endline). In addition, the quality of counseling support to caregivers, at health facilities and through home visits, will be assessed at baseline and endline in a cohort of CHWs recruited from the MRV-CCD full intervention group. Figure 2a provides an overview of the research design for objectives 1 and 2. Figure 2b provides an overview of the research design for objective 3.

[figure not shown]

Figure 2a. Research design overview – community component

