The study includes enumeration of all households in probability selected geographical units (national census enumeration areas) in catchment villages of selected health facilities, about 12-16 per intervention group. All households with resident caregivers of children 0-24 months of age will be eligible for recruitment into the caregiver cohort. Data collection includes two stages of recruitment/participation at baseline, whereby an eligible caregiver will complete a radio listenership survey during the household enumeration exercise, and will then be recruited into the caregiver cohort at a separate visit. Those consenting to the caregiver cohort will complete a detailed home-based caregiver survey at baseline and the same people will complete the listenership and caregiver surveys at endline. Table 1 provides an overview summary of data gathering activities.

[figure not shown]

Figure 2b. Research design overview – community health worker component

Table 1. Data gathering activities

Abbreviated Objective	(1) Caregiver radio listenership patterns, exposures, and effect on caregiver ECD perceptions, knowledge and reported parenting practices nine months post-intervention	(2) Effect of Malezi II full intervention (MRV-CCD) on caregiver's knowledge and parenting behaviors/practices compared to MR intervention	(3) Effect of short video job aids on the quality of counseling provided by the CHW in the clinic and the home (4) CHW perspectives and experiences with use of the short videos as a job aid (5) Caregiver perspectives and experiences with CHWs, short videos, and ECD services in the health facility.
Design	Two-arm pre/post intervention cohort(s) design About 30 health facility catchment communities (1) 12-16 facilities – MR intervention (radio messaging only) (2) 12-16 facilities – MRV-CCD augmented intervention (radio, video job aids, CCD package)		Pre/post cohort, intervention MRV-CCD group only 12-16 health facility catchment communities selected for the Malezi II evaluation study in MRV-CCD group Qualitative component with CHW FGDs and caregiver IDIs

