The radio messaging in both intervention groups, and the short videos in the second intervention group (only) will be introduced after the baseline assessment of the caregiver cohort. The exposure period for the two interventions, as described in Table 2, will be for nine months, followed by the endline assessment of caregivers.

Table 2. Description of intervention packages in two study arms

Intervention group	Description and expected exposure (dose)
Malezi II minimum package Radio (MR)	Radio messaging spots Dose: Up to 35-40 different messages, 3 stations aired on (2 regional, 1 national), about 10 times per day; 7 days per week airing frequency; 9 months duration of exposure 
▪ Caregiver exposure to radio messaging during 9-month period: currently unknown, but estimated at 50% of caregivers hearing about 7 messages/week.
Malezi II full package Radio, Video Job Aids, CCD program (MRV-CCD)	Radio messaging spots 
▪ Same as MR group

MRV-CCD	
Short video ECD job aids (with training)
 
Five short ECD mobile films (videos) of 3-5 minutes each will feature a mixture of real-life testimonies and scripted interactions between health workers and caregivers, and demonstrations of caregivers stimulating their young child. Each video will show a range of age-appropriate ECD practices that encourage child development (play; communication; positive caregiver-child interaction; safe/stimulating environment; positive discipline), illustrating skills and providing knowledge. All videos will have some cross-cutting content, emphasizing the general benefits of ECD activities during the early years, and one video will be devoted exclusively to cross-cutting parental guidance on developmental milestones and benefits of applying ECD practices. Four videos will target specific age groups (0-5, 6-11, 12-23, >=24 months).
 
Caregiver exposure to group counseling at clinic is estimated to be 2-4 sessions in a 9-month period
 
Caregiver exposure to individual counseling at home is estimated to be 3-6 sessions in a 9-month period

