Only caregivers who have consented to participate in the study cohort will be visited for CHW observations. On arrival at the caregiver's home, the RA will first remind the participant about the study and reconfirm caregiver consent to being observed by the RA and video-recorded during the session before the CHW proceeds with the home visit observation. Caregivers will be free to decide not to be observed, or to allow observation without video recording, without penalty; the CHW counseling session will proceed with or without these evaluation components. The home sessions will last about 10-60 minutes.

Outcome and Measures: CHW Cohort

Outcomes characterizing CHW capacity and the quality of CHW-caregiver interactions, and how CHW capacity and mentoring skills may change between baseline and endline after introduction of ECD videos, are grouped into four main categories:

1. CHW knowledge: of ECD and early stimulation
2. Compliance with message delivery: How well does the CHW demonstrate clear communication of ECD messages?
3. Responsiveness and listening skills: Does the CHW demonstrate good listening and communication skills, establishing good rapport and showing empathy?
4. Acceptability of videos: Whether CHW report video job aid to be useful, user friendly and acceptable and whether any challenges with use were observed or reported.

Given their potential to modify CHW capacity to deliver the intervention, the following characteristics and standard assessments will also be completed with CHW.

IQ - Ravens Standard Progressive Matrix (Ravens): Refer to above description.

Mental health, depression/anxiety (PHQ-9, GAD-7): Refer to above description.

CHW reported activities: The intensity and frequency of CHW responsibilities (e.g. number of households visited, frequency of visits) will be assessed in the pre/post structured interviews, as well as CHW training and duration of working as a CHW.

Media listenership: Questions from the caregiver listenership will be included in the CHW baseline/endline questionnaires, assessing exposure to radio communication, and recall of health education messages (including ECD-related) with respect to content, and source.

Scoring observations of CHW sessions

Video observations will be coded and scored by trained staff using a standardized checklist, and a sample of 20% of all videos will be double coded by another trained member of the study team to ensure reliability of coding.

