Observation checklists for each CHW, by type of observation (clinic, home) and timing of observation (baseline, endline), will be averaged across all measures. Thus, a CHW's baseline or endline home score will be the average score of the in-person observation checklist scores (2 data points) and the video scores from two home visits (2 data points). A CHW's clinic score at baseline or endline will be

the average of two data points, based upon the in-person observation checklist scores at two clinic sessions. Each checklist score will impute missing values as the mean score for other values in that section, and an observation with more than 20% missing values will be considered invalid (and should be re-done).

Process Evaluation: MRV-CCD Group

The primary purpose of the process evaluation is to establish the fidelity of CHWs to the full Malezi II intervention package, specifically monitoring CHW practices and use of the short videos throughout the intervention period. The process evaluation component will also systematically collect routine program monitoring data from the MRV-CCD index facilities and CHWs with respect to developmental referrals made, number of group session held, and number of CHW home visits reported.

During the 9-month exposure period, research associates will aim to conduct CHW observation checklists (as designed for the baseline/endline data collection) on each MRV-CCD group CHW at least once/quarter for clinic sessions and twice/quarter for home sessions. This translates to about 246 home and 123 clinic checklists completed per quarter (total 369), or about 185/RA/quarter, or roughly 3 per day.

Focus group discussions

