Quantitative evaluation of the effect of the short videos on quality of CHW counseling will follow similar analyses as described above, including characteristics of the population, and statistical comparison of outcomes at baseline and endline (post-video introduction) within the CHW cohort. Some qualitative analyses will also be done to describe and summarize CHW opinions and suggestions regarding video content, design and use.

The audio-recorded FGDs with CHW will be transcribed and translated from Kiswahili to English by qualitative researchers. Transcripts will be reviewed by a member of the study team is in fluent in English and Kiswahili. Transcripts will be imported into a qualitative software program for analysis (MAXQDA or similar program). A codebook will be developed with deductive codes based questions in the FGD guide with inductive codes added during the coding process as needed. Study team members trained in coding skills will be responsible for coding the transcripts. A study investigator will review a subset of transcripts to ensure consistency across different coders.

Objectives 4-5: FGDs with CHWs and IDIs with caregivers

Qualitative data will be summarized through descriptive, text-based summaries by code. Textual data will be carefully read by investigators to identify recurrent patterns and themes, and to draw conclusions from issues connected to the study questions. Themes may include acceptability of CHW home visitation or use of the videos, perceptions of CHW authority on ECD/parenting, experiences with health provider counseling on ECD at health facilities, and recommendations for improving ECD education and interventions.

ETHICAL CONSIDERATIONS

No data collection will be done prior to approval of this protocol by the National Research Ethics Committee of the National Institute of Medical Research and the Advarra Institutional Review Board

in the USA. Research participants will only join the study after their informed consent has been obtained. This study will be registered with a clinical trials network.

Informed Consent

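### Objective 3 reads the CHW pre-post change as the effect of the video job-aid package, but radio starts alongside it and there is no comparison group of CHWs, so only the combined change can be concluded

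*Protocol*

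**What the plan says.** The question is about the videos. Under Research Questions the protocol asks: "Do the Malezi II video job aids improve the quality of CHW ECD counseling support given to caregivers in clinic and home settings". Objective 3 asks the same of introducing the videos, and counts training, provision and supportive supervision as part of that introduction. Aim 3 names Malezi II training together with the video job aids.

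The analysis has one group. Data Analysis, Objective 3, says that "Quantitative evaluation of the effect of the short videos on quality of CHW counseling will follow similar analyses as described above", including "statistical comparison of outcomes at baseline and endline (post-video introduction) within the CHW cohort". Table 1 describes the design as "Pre/post cohort, intervention MRV-CCD group only", and the CHW recruitment section confirms that no CHWs are enrolled from MR facilities.

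Radio starts over the same period. Intervention Description says: "The radio messaging in both intervention groups, and the short videos in the second intervention group (only) will be introduced after the baseline assessment" (the sentence goes on to refer to the caregiver cohort). Exposure to both lasts nine months, and Table 2 gives the MRV-CCD group the same radio as the MR group. Table 1 lists radio and video as the caregiver exposure but only video use as the CHW exposure.

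The protocol expects that CHWs may hear the radio. Outcome and Measures: CHW Cohort plans a media listenership module for CHWs at baseline and endline, "assessing exposure to radio communication, and recall of health education messages (including ECD-related) with respect to content, and source", among characteristics that could modify their capacity.

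**The concern.** A pre-post change in one cohort is the sum of everything that changed between the two measurements. Here at least two program components start after baseline, radio and the video package, and the text credits the change to one of them. With CHWs enrolled only where both are delivered, no contrast in the planned data removes radio or time.

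This matters because the policy section says that the contribution of the videos to CHW skills will inform scale-up of digital job aids. A gain due partly to radio, trend or observation would be passed to decision makers as a result for the videos.

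**Working it through.** **1. Passages side by side**

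| Element | Protocol | Consequence |
|---|---|---|
| Effect named | Video job aids with training, provision and supervision (Objective 3, research question, Data Analysis) | A claim about one component |
| Comparison | Baseline against endline in one cohort (Table 1, Data Analysis) | Estimates total change |
| Started after baseline | Radio and videos, nine months each (Intervention Description, Table 2) | Both lie inside the total change |
| CHW exposure listed | Video use only (Table 1) | Radio left out of the CHW component |

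The timing sentence refers to the caregiver baseline. That the CHW baseline also precedes radio is an inference, though a sound one. Table 1 gives both components the same order: a 2-3 month baseline, a month of CHW training, then nine months of exposure. Homes for CHW observation are also drawn from the enrolled caregiver cohort.

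**2. Repeated observation.** The process evaluation aims to observe "each MRV-CCD group CHW at least once/quarter for clinic sessions and twice/quarter for home sessions", using the baseline/endline checklist. Its own count is 246 home + 123 clinic = 369 per quarter, and 369/123 = 3 per CHW. Over three quarters that is 9. With 2 clinic and 2 home sessions at baseline, 13 sessions are planned before endline.

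**3. The planned sample size is arithmetically right.** Table 5 inputs: 50% to 65%, correlation 0.4, McNemar's test at 5% (two-sided reproduces it), 80% power.

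- Shared term: 0.4 × √(0.50 × 0.50 × 0.65 × 0.35) = 0.0954
- Discordant cells: 0.50 × 0.35 − 0.0954 = 0.0796, and 0.65 × 0.50 − 0.0954 = 0.2296; sum s = 0.3092, difference d = 0.15
- n = [1.960 × √s + 0.842 × √(s − d²)]² / d² = [1.960 × 0.5561 + 0.842 × 0.5355]² / 0.0225 = 105.5, so 106
- Adjusted: 106 × 1.1 / 0.95 = 122.7, so 123

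Both figures match the protocol; the other two rows of Table 5 also reproduce (102/118 and 78/90). But d is the whole pre-post change. The calculation powers detection of any change, whatever its cause.

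**4. What the test does when the videos do nothing.** The power expression is Φ{[d√n − 1.960√s] / √(s − d²)}, with effective n = 106, baseline 50% and correlation 0.4. The non-video rise is an assumption, shown as a range because the protocol gives no value.

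| Assumed non-video rise | Chance of a significant increase |
|---|---|
| 0 points | 2.5% |
| 2.5 points | 7% |
| 5 points | 15% |
| 10 points | 46% |
| 15 points | 80% |

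**The case against.** **Training and supervision are part of what is being tested.** This stands. Aim 3 and Objective 3 include them, so they are not confounders. Radio, trend and repeated observation remain outside the package.

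**The single-arm design is stated openly, and elsewhere the protocol describes the MRV-CCD group in joint terms.** Also true. The overview of the Malezi II program sets the group's pre-post contrast against CCD support alone: "compared to CCD program support without radio and short video support". A reader might infer that this directly contradicts Objective 3. It does not: that paragraph concerns caregiver outcomes. It is a good model for the wording, not proof of an inconsistency.

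**Radio exposure is measured, and regression is allowed.** Covariate adjustment is optional in the caregiver section that Objective 3 follows. It might reduce confounding by a CHW's own listening. It cannot remove radio acting through caregivers and communities, or trend, and it cannot supply the missing comparison group.

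**Radio may do little to observed counseling skill.** This is fair. The example checklist items concern listening and prompting the caregiver, radio is aimed at caregivers, and the background section calls effects of information-only programs for parents relatively small. The case for radio is strongest for CHW ECD knowledge.

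**Learning from repeated scoring is speculative.** A reader might infer that 13 sessions train the CHWs to the checklist. The quarterly observations are an aim, and nothing says that CHWs see their scores. Repeated observation is an influence that the design cannot exclude, not one shown to operate.

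**Conclusion.** The point holds as a limit on what may be concluded. Objective 3 can show that CHW knowledge and counseling quality changed after radio and the video package were added to CCD. It cannot assign that change to the video package. This follows from the design and needs no numerical assumption.

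The size of the misattribution is unknown. A reader might want to say what share of the planned 15-point change comes from radio or observation; the protocol offers no basis for such a figure. The 15% and 46% above show only how the planned test behaves if a 5- or 10-point non-video rise is assumed.

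A reader might also infer that planned data could isolate the videos, through the quarterly scores in sequence or endline sessions with and without video use. They could not. Every quarterly score falls within the exposure period shared with radio, and whether a session uses a video depends partly on the CHW.

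**What to change.** 1. Restate Aim 3, Objective 3, the matching research question and the Objective 3 analysis text along these lines: *the change from baseline to endline in CHW ECD knowledge and counseling quality after radio messaging and the video job aids, with their training, provision and supervision, are added to the established CCD program.* State that no video-only effect will be concluded.
2. List radio messaging as a CHW exposure in Table 1.
3. Compute the pre-post checklist score only on items scored at both times. Data Collection: CHW Cohort says that the endline checklists add video-use items that do not apply at baseline; including them would change what the score measures.
4. Report the change by CHW radio listenership and message recall, as supportive description only.

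The cost is wording, one scoring rule and one table from data already planned. The real loss is a less specific claim for the videos.

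An MR cohort of CHWs is not needed for this correction and would not fully isolate the videos, because MR CHWs work without the CCD program. It would also need more CHWs. Assume a 50% baseline and correlation 0.4 in both groups, a 15-point change in MRV-CCD and none in MR. The variances of change are then 0.2867 and 0.3000, so n per group = (0.2867 + 0.3000) × (1.960 + 0.842)² / 0.15² = 205. With 106 per group, power would be 52%.
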